- Rationale for excluding of EDB4 from primary analysis: As shown in Table 3, the patient identification period in EDB4 starts on 10/01/2018 which is after the official approval of osimertinib for 1L metastatic EGFRm+ NSCLC. This means there are limited "control" patients captured in EDB4 from the pre-osimertinib era (see Figure 15). Given the documented clinical benefit and the corresponding rapid uptake of osimertinib after April 2018, it could be assumed that patients who initiated the "old" standard-of-care after April 2018 did so for specific reasons. This means these patients may be likely to be significantly different in their baseline characteristics and prognosis for reasons that may not be measurable.

For these reasons, only EDB1 will be used for the main analysis. However, EDB2 and EDB4 will be considered as part of a sensitivity analysis in which all databases are individually analyzed and treatment effect estimates are pooled using a meta-analytic fixed effects model (see sensitivity analysis #11 in Table 9).

Data source provenance/curation: In brief, all databases provide EHR-derived oncology-specific patient-level information which are either derived directly (e.g., through structured data fields and dropdown menu selections) from EHR and/or undergo semi-automated abstraction processes from unstructured reports. The detailed data provenance, abstraction processes and implemented business rules to curate and prioritize certain variables may vary by database and can be found in legacy publications by the data partners.

Table 3. Metadata about data sources and software.

ie 5. Metadata about data soui	EDB1	EDB2	EDB4
Data Source(s):	EHR-derived	EHR-derived	EHR-derived
Study Period:	Patient identification period: 01/01/2011-04/30/2024 with follow-up information through data cut-off date on 04/30/2024	Follow-up information through 02/24/2023 (there is no specific time period restrictions for patient eligibility)	Patient identification period: 10/01/2018-09/30/2023 with follow-up information through data cut-off date on 09/30/2023.
Eligible Cohort Entry Period:	Anytime at start of study drug initiation	Anytime at start of study drug initiation	Anytime at start of study drug initiation
Data Version (or date of last update):	Delivery: Jul 11, 2024	Delivery: Sep 8, 2023 Updated (LoT addition): Mar 11, 2024	Delivery: Oct 24, 2023 Updated (demographics): Feb 29, 2024

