To estimate the treatment effects for osimertinib using propensity score matching across imputed datasets we will apply the "within" approach using the "MatchThem" R package. 28,29 That is, propensity score matching and the estimation of the treatment effect are performed in each imputed dataset separately and resulting treatment effect estimates are combined using Rubin's rule. In this study, this will be implemented by matching eligible patients on their propensity to initiate osimertinib using a 1:1 nearest neighbor matching algorithm without replacement and a caliper of 1% of the standard deviation of the propensity score. The resulting covariates balance will be assessed by computing and visualizing ASMDs before and after matching across datasets. As compared to a single dataset matching approach, this can lead to a range of ASMDs per covariate due to random variation across imputed datasets for which an example (using simulated data) is illustrated in Figure 5. If sufficient balance can be established, a Cox proportional hazards regression model will be fit to estimate the marginal average treatment effect in the matched population. Since in most databases there are more osimertinib patients than patients in the control arm, the estimand will rather correspond to the ATC than the ATT. Confidence intervals will be estimated using cluster-robust standard errors. 30 As a secondary endpoint, we will additionally estimate the median OS survival time difference between the two exposure groups using the Kaplan-Meier method. It should be noted that due to administrative and de-identification purposes, the date of death is often only available at the month- or year-granularity level, in which case the date of death will be imputed to the 15th of a month or July 2nd of a year, respectively (depending on the database). In rare cases, this can lead to negative/implausible follow-up times if the date of death is very close to the index date. These patients will be excluded from the analysis.

The final hazard ratio and median OS survival time difference estimates for each database will then be combined using Rubin's rule.^{27,31} To arrive at a single estimate across databases, the final estimates will be summarized through a meta-analytic fixed effects model.³² A summary of the analytic approach is summarized in Table 7 and an example workflow with simulated data and annotated code can be found https://example.com/here/beta-arrive

A. Primary analysis

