Sensitivity #1	Caliper matching on ROPRO prognostic score instead of propensity score	Matching patients on validated prognostic score may be more beneficial to control for (unmeasured) confounding	Matches patients on validated prognostic score that incorporates weights of key prognostic factors	Limited experience on how to optimally use prognostic scores and should be seen as an experimental sensitivity analysis
Sensitivity #2	ATO weighting instead of matching	Weights that resemble the average treatment effect in the overlap population (ATO) create a clinical equipoise population which is comparable to an RCT	ATO weighting usually results in excellent balance and clinical equipoise	Estimates the average treatment effect among the overlap patients which may not be comparable to target population anymore
Sensitivity #3	SMR/ATT weighting instead of matching. Here symmetric trimming (i.e., setting all weights lower/higher than that at a given quantile to the weight at the quantile) of extreme weights may be considered with the quantiles chosen based on weight distribution and resulting balancing performance.	SMR weighting retains all patients and resembles the same estimand as matching	ATT weighting retains all patients	Patients with extreme weights after trimming may bias the analysis
Sensitivity #4	Censoring date is changed to 3 months before data cut- off date	For all databases, information on mortality comes from different data sources which are updated asynchronously. To account for the potential lag of updated mortality information (ghost-time	Approach implements a more conservative censoring rule	Approach addresses ghost-time bias by censoring patients without a recorded

		bias ³³), the censoring date for patients without mortality event in the whole patient identification period will be moved to last sign of patients being alive/visit or 3 months before data cut-off date, whichever occurred earlier. ³⁴		death event earlier
Sensitivity #5	Delta imputation models for MNAR (tipping point analysis)	Primary multiple imputation analysis assumes MAR which may not hold for every covariate	Estimates impact of deviations from MAR assumption on final treatment effect estimates for key covariates	Delta parameters must be assumed and results are complex to interpret in multivariate missingness settings; just must important covariates or those with highest suspicion of being MNAR will be evaluated

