- Balancing patients on calendar year is not possible since calendar year shows instrumental variable-like behaviours (see Figure 13), i.e., it perfectly predicts treatment assignment and does not have any association with the outcome other than through the exposure. This assumption is formally untestable but clinically reasonable since there has not been any other significant change in treatment paradigms for FLAURA-like EGFR-mutated NSCLC populations other than introduction of osimertinib. The improvements of radiation of brain metastases may be the only exception, but it is expected that this may be of negligible significance for the scope of this emulation.

• Proportions of Asian race and patients with smoking history is different in the used US-only EHR-derived databases and the FLAURA trial population which can lead to altered treatment effect estimates since race was found to be an effect modifier in the trial's subgroup analyses. This limitation is address in sensitivity analysis #7 by re-weighting the distribution in these covariates to match that of the FLAURA populations.

8. Protection of human subjects

This study has been approved by the Brigham and Women's Hospital Institutional Review Board.

9. References

- 1. Jm F, A P, D M, et al. Nonrandomized Real-World Evidence to Support Regulatory Decision Making: Process for a Randomized Trial Replication Project. *Clin Pharmacol Ther*. 2020;107(4). doi:10.1002/cpt.1633
- 5. Soria Jean-Charles, Ohe Yuichiro, Vansteenkiste Johan, et al. Osimertinib in Untreated EGFR-Mutated Advanced Non–Small-Cell Lung Cancer. *N Engl J Med*. 2018;378(2):113-125. doi:10.1056/NEJMoa1713137

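### Sensitivity #3 (SMR/ATT weighting) is presented as keeping the estimand of matching, but section 6.7.1 says the matched estimand is nearer the ATC than the ATT

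*Protocol*

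**What the plan says.** Section 6.7.1 of the Protocol defines the primary analysis as 1:1 nearest-neighbour matching without replacement on the propensity to initiate osimertinib, with "a caliper of 1% of the standard deviation of the propensity score". A Cox model then estimates the marginal effect in the matched population. The section explains that "in most databases there are more osimertinib patients than patients in the control arm" and concludes that "the estimand will rather correspond to the ATC than the ATT".

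Table 9, Sensitivity #3, replaces matching with SMR/ATT weighting, possibly with trimming of extreme weights. Its rationale is that "SMR weighting retains all patients and resembles the same estimand as matching". The only limitation it lists is "Patients with extreme weights after trimming may bias the analysis".

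The row above, Sensitivity #2 (ATO weighting), does declare a change of population: "Estimates the average treatment effect among the overlap patients which may not be comparable to target population anymore".

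Section 6.1.1 adds that "only EDB1 will be used for the main analysis".

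**The concern.** The propensity modelled is that of starting osimertinib, so ATT (SMR) weights standardise to osimertinib initiators. Section 6.7.1 says matching leans the other way, towards SoC initiators. The two sentences name opposite targets for the same primary analysis.

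This affects how #3 is read. Table 9's last column is for limitations relative to the primary analysis, and row #2 shows that the authors count a changed target population as one. Row #3 omits it and asserts sameness instead. The protocol also accepts that effect modification can move the estimate: the rationale for Sensitivity #7 says so, section 7 states that "race was found to be an effect modifier", and Table 7 marks age, race/ethnicity and ECOG as subgroups with significant differences in FLAURA. If such a modifier is distributed differently in the two arms, #3 and the primary result can differ with confounding controlled equally well in both. The stated rationale would lead a reader to put that difference down to method alone.

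**Working it through.** **Step 1: what each method targets.** Let e be the probability of initiating osimertinib.

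- ATT/SMR weights: osimertinib 1, SoC e/(1−e). The target is osimertinib initiators.
- ATC weights: SoC 1, osimertinib (1−e)/e. The target is SoC initiators.
- 1:1 matching without replacement: the matched set resembles the smaller arm, because that arm is nearly used up. If osimertinib is larger, this is towards the ATC, as section 6.7.1 says. A tight caliper also drops some of the smaller arm, so the match to ATC or ATT is only approximate.

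The rationale of #3 therefore agrees with section 6.7.1 only if the ATT and ATC coincide.

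**Step 2: where the matched set falls.** The readable text gives no arm sizes, so all inputs here are assumptions.

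*Exact matching on one binary modifier.* Overall prevalence is 40%, the log-odds of osimertinib is 0.8 for carriers, and stratum HRs are 0.9 (non-carriers) and 0.6 (carriers). The average HR in a population with modifier share s is exp[(1−s)·ln 0.9 + s·ln 0.6].

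| Osimertinib : SoC | Share in ATT | Share in ATC | Share matched | HR ATT | HR ATC | HR matched |
|---|---|---|---|---|---|---|
| about 1:1 | 49.6% | 30.6% | 37.9% | 0.736 | 0.795 | 0.772 |
| about 2:1 | 46.2% | 27.8% | 27.8% | 0.746 | 0.804 | 0.804 |
| about 3:1 | 44.6% | 26.6% | 26.6% | 0.751 | 0.808 | 0.808 |

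*Greedy matching with the 1% caliper.* Simulated propensity scores with c-statistic 0.65 to 0.71, 20 replicates, modifier prevalence 30% in osimertinib (ATT) and 50% in SoC (ATC).

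| Osimertinib / SoC | Smaller arm matched | Prevalence in matched set | Nearer to |
|---|---|---|---|
| 1,500 / 600 | 83–89% | about 44–45% | ATC |
| 1,000 / 800 | 69–76% | about 40% | midway |
| 600 / 1,500 | 84–91% | about 32–34% | ATT |

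Both exercises support the reasoning in section 6.7.1 when osimertinib is clearly the larger arm. The second also shows that the answer reverses if SoC is clearly larger.

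**Step 3: size of the ATT–ATC gap.** As an approximation, the ratio of the two HRs is exp[(prevalence gap between arms) × ln(ratio of stratum HRs)].

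| Prevalence gap | Stratum HR ratio 1.25 | Stratum HR ratio 1.5 |
|---|---|---|
| 0.05 | 1.011 | 1.020 |
| 0.10 | 1.023 | 1.041 |
| 0.20 | 1.046 | 1.084 |

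If the prevalence gap is 0 or the stratum HR ratio is 1, the result is 1.000. The largest entry corresponds to about 0.80 against 0.80/1.084 = 0.74.

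**Step 4: scale.** Section 10.3 gives 80% power at HR 0.8 and two-sided alpha 0.05 but, in readable text, no event count. The figure can therefore be inverted but not reproduced.

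- Schoenfeld events at 1:1: 4 × (1.960 + 0.842)² / (ln 0.8)² = 630.5, about 631.
- Standard error of the log HR: 2/√630.5 = 0.080.
- 95% CI around 0.80: 0.80 × exp(±1.96 × 0.080) = about 0.68 to 0.94.

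Even the largest illustrated shift lies inside that interval.

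**The case against.** The strongest objection is that the conflict is not shown for the database that matters. Section 6.7.1 speaks of most databases, and EDB2 and EDB4 alone could make that true among three. EDB1 identifies patients from 2011, so it includes years before first-line osimertinib, and its arm counts are not readable here. If SoC is the larger arm in EDB1, matching leans to the ATT and the rationale of #3 is sound for the primary analysis. This stands, but it only moves the error: the unqualified ATC statement would then misdescribe the primary analysis. If the arms are similar, neither label fits well. One of the two sentences needs changing in every case.

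Second, both sentences are hedged, and the formal target is simply the matched population. That is fair, but the hedges still point in opposite directions.

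Third, the consequence needs a modifier that differs between arms within EDB1, and no readable text shows one. The remark on race in section 7 compares US databases with FLAURA. The same section argues that calendar time drives treatment choice, which would make the two arms' populations similar. This also stands: the gap may be close to zero, and the illustrative inputs have no source in the document.

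Fourth, #2, #7 and the subgroup interaction models also bear on heterogeneity, and ATT weighting is legitimate in itself. Both points are true, but neither corrects what row #3 tells its reader.

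**Conclusion.** The concern holds. The protocol gives two incompatible accounts of what matching estimates, and row #3 omits a limitation that row #2 declares for the same kind of change. The inconsistency in the text is certain. Which sentence is wrong for EDB1 depends on arm sizes that cannot be read here.

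The practical effect is limited to interpreting one sensitivity analysis. Over the assumed range, the ATT and ATC hazard ratios differ by 1.1% to 8.4%, and by nothing if the effect is homogeneous or the arms share the same modifier distribution. Agreement between #3 and the primary result would still reassure. The primary estimate and the power figure do not change. It should be corrected before #3 is used as a robustness check.

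**What to change.** Confirm which arm is larger in EDB1 and state in section 6.7.1 the matching target for that database. Then:

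- **Osimertinib larger:** use ATC weights in #3 (SoC 1, osimertinib (1−e)/e) as the closer like-for-like check, and note that the 1% caliper makes the matched population only approximately ATC. Alternatively, keep ATT weights, delete the same-estimand claim and list the change of target population as a limitation, as row #2 does.
- **SoC larger:** correct the ATC statement in section 6.7.1 for EDB1. The ATT rationale in #3 can then stand, with the same note on the caliper.
- **Arms similar:** describe the target as the matched population, without an ATT or ATC label, and list the changed population as a limitation in #3.

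The cost is one row of Table 9 or one sentence of section 6.7.1 and, if the weights change, one estimand argument in the weighting call. No further data are needed.

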6.6.5. Context and rationale for outcome(s) of interest

The primary outcome for the database study was defined to emulate the primary outcome for the trial, time from index to death due to any reason (overall survival). Operational definitions:

- EDB1: Time in {days, months and years} from index date to death due to any reason. The date of death is de-identified to month-level granularity or (rarely) to year-level granularity and the date of death is therefore imputed to the 15th of a month or mid-year/July 2 of the year of death, respectively. In If there is no indication that a patient died during the study period, the patient is censored. The censoring date is defined as the last visit or treatment encounter or data cut-off date, whichever occurred earlier. The overall survival endpoint is operationalized using a parameterized R function edb1_get_os() and more details can be found in the attached pdf documentation.
- EDB2: Time in {days, months and years} from index date to death due to any reason. If there is no indication that a patient died during the study period, the patient is censored. The censoring date is defined as the last observed activity date or data cut-off date, whichever occurred earlier. Activity dates are defined as documented in Table 4. Dates used to derive time to all-cause mortality may have some associated imprecision such that the date of death is either known completely, the year and month is known or only the year is known. The overall survival endpoint is operationalized using a parameterized R function edb2_get_os() and more details can be found in the attached pdf documentation.

Table 4. Relevant clinical activities considered to derive last activity date for censoring.

Table / clinical activity considered	Dates considered
Adverse events	Event date
Therapy (cellular, systemic, radiation, surgery)	Start and end dates or declined intervention date, surgery date, assessed resection dates
Palliative care referral	Referral date
Visits	Contact/visit date
Vitals	Assessed date
Labs	Lab date
Biomarkers	Specimen collection date
Patient observation period	Start and end dates
Demographics	Date of most recent contact with provider, date patient was diagnosed with a second primary malignancy
Performance assessments	Documented date, reported date

[figure not shown]
Secondary diagnoses	Diagnosis date
Progression, histology, lymphovascular invasion, metastatic sites, pancoast tumor, perineural invasion	Assessed date

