Sensitivity #6	Restrict to patients with Exon19 deletion only (databases for which this information is available)	FLAURA only included patients with sensitizing mutation (Exon19 deletion) but this information is not consistently provided across databases which is why in primary analyses we include all patients with any EGFR mutation assuming that it is sensitizing given that these patients initiated osimertinib, gefitinib or erlotinib	Target population is genetically more identical and increases specificity of biomarker measurement	Information not consistently available
Sensitivity #7	Re-weighting of strong risk factors and/or treatment effect modifiers distribution to match that of FLAURA	In the presence of effect modification, treatment effect estimates may be different if	Re-weighting adjusts for differences in distributions of key risk factors and/or	Re-weighting risk factors/potential

		the distribution of strong risk factors/effect modifiers is different in the emulated cohort versus the trial cohort	treatment effect modifiers (see subgroup analysis in Table 7)	effect modifiers to match the FLAURA trial and simultaneously balancing them across treatment groups may be challenging due to differences in measurement
Sensitivity #8	Including patients who have had at least 1 visit 90 days prior to treatment initiation	EHR are often lacking data continuity, and this analysis uses the requirement of 1 visit as a proxy for continuous observation periods	Considers aspect of data continuity	There may be patients who are put on treatment immediately in which case they are falsely excluded
Sensitivity #9	Exclusion of patients with osimertinib exposure before April 18, 2018	There are a few patients who are observed to have received osimertinib before its official approval (potentially due to off-label use in 1L, compassionate use, etc.)	Limits chances of exposure misclassification	May exclude truly eligible patients
Sensitivity #10	Restriction of eligible calendar time period from 2015 to 2022	Descriptive analyses indicate that there was a rapid uptake of new initiators of osimertinib immediately after approval in 2018 and a sudden decrease of SoC TKIs. This means there is hardly any overlap of patients pre/post 2018 and calendar cannot be sufficiently balanced	This sensitivity aims to mitigate the potential effects by imbalance in calendar time	Calendar time will overall remain imbalanced

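### Sensitivity #4 censors only survivors 3 months earlier and still counts deaths in that window, so it raises the HR by nearly the same amount whether or not deaths are reported late

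*Protocol*

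**What the plan says.** Protocol Table 9 (section 6.7.1) gives the purpose of Sensitivity #4 as "To account for the potential lag of updated mortality information", which it identifies with ghost-time bias. The rule is that "the censoring date for patients without mortality event in the whole patient identification period will be moved" to the earlier of the last sign of life and 3 months before data cut-off. The strengths column reads "Approach implements a more conservative censoring rule". The limitations column begins "Approach addresses ghost-time bias by censoring patients without a recorded" and says that these patients are censored earlier.

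Three other places matter:

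- **Table 3, EDB1:** "Patient identification period: 01/01/2011-04/30/2024 with follow-up information through data cut-off date on 04/30/2024". The identification period ends on the cut-off date itself.
- **Section 6.6.5, EDB1, patients with no recorded death:** "The censoring date is defined as the last visit or treatment encounter or data cut-off date, whichever occurred earlier".
- **Calendar time:** the row for Sensitivity #10 in Table 9 says "there is hardly any overlap of patients pre/post 2018". Section 7 says of calendar year that "it perfectly predicts treatment assignment".

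**The concern.** A patient who dies in the last 3 months has a mortality event within the identification period and so is not re-censored. The death and the time leading up to it stay in. A patient alive in the same 3 months loses that time. Whether the time counts thus depends on the later outcome. Nothing in the protocol drops deaths after the new date.

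The rule also misses its target. The EDB1 primary analysis already stops patients without a recorded death at their last encounter, so a patient whose death is unrecorded adds no time after that encounter. Sensitivity #4 recovers no late-reported death. It keeps the events of the primary analysis and removes time during which patients were known to be alive.

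Because the arms are nearly separated in calendar time, follow-up close to April 2024 is mainly osimertinib follow-up. Removing survivor time there raises the osimertinib death rate and the HR. The study judges concordance with a trial HR of 0.80 (sections 2 and 4), so an upward shift that the rule itself creates could be taken as a sign that reporting lag had flattered osimertinib.

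**Working it through.** **Inputs from the protocol.** SoC median OS 31.8 months and HR 0.80 (section 4); EDB1 identification from 01/01/2011 and cut-off 04/30/2024 (Table 3); osimertinib available from April 2018 (section 4); 1:1 matching; 80% power at HR 0.80 and two-sided alpha 0.05 (section 10.3).

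**Assumed, because the protocol gives no readable figure.** Accrual by calendar time, gap between last visit and cut-off, reporting lag, and loss to follow-up. Only differences between analyses should be read; the HRs are not predictions for this study.

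**Yardstick.** The event count is not readable in the text, so the stated 80% power cannot be checked directly. The events it implies are 4 × (1.96 + 0.8416)² / (ln 0.8)² = 631, giving a standard error of log HR of 2/√631 = 0.080.

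**Hand calculation, no lag.** Take constant hazards: SoC ln 2/31.8 = 0.02180 per month; osimertinib 0.8 × 0.02180 = 0.01744. Let osimertinib patients start uniformly over the 72 months before cut-off, and SoC patients uniformly from 160 to 72 months before it (January 2011 to April 2018).

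- Share alive at cut-off: osimertinib (1 − e^(−72 × 0.01744))/(72 × 0.01744) = 0.570; SoC (e^(−72 × 0.02180) − e^(−160 × 0.02180))/(88 × 0.02180) = 0.093.
- Mean time at risk, (1 − share alive)/hazard: 24.69 and 41.63 months.
- With a last visit on average 0.5 months before cut-off, the primary rule gives 24.69 − 0.5 × 0.570 = 24.40 and 41.63 − 0.5 × 0.093 = 41.58.
- Sensitivity #4 removes a further 2.5 months per survivor, 1.42 and 0.23 months per patient, leaving 22.98 and 41.35. Events are unchanged.
- The rate ratio is multiplied by (24.40/22.98)/(41.58/41.35) = 1.062/1.006 = 1.056, or +0.054 in log terms, although there is no lag.

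**Simulation with a Cox model.** 400,000 patients per arm, true HR 0.80, 128 scenarios: four osimertinib accrual patterns; last visit uniform within 1 or 3 months; lag from none to exponential with mean 6 months, or 0/50/80/100% of last-3-month deaths unrecorded; with and without 1% monthly loss. The symmetric cut ends everyone's follow-up 3 months before cut-off and ignores later deaths. Two settings without loss, with log shifts from the primary:

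| Setting | Lag | Primary HR | #4 HR | Symmetric HR | Log shift, #4 | Log shift, symmetric |
|---|---|---|---|---|---|---|
| Accrual to April 2024, 1-month gap | none | 0.811 | 0.863 | 0.801 | +0.062 | −0.012 |
| | all deaths in window unrecorded | 0.752 | 0.801 | 0.801 | +0.063 | +0.063 |
| | mean 1 month | 0.791 | 0.842 | 0.800 | +0.062 | +0.011 |
| | mean 3 months | 0.753 | 0.802 | 0.779 | +0.063 | +0.034 |
| | mean 6 months | 0.700 | 0.744 | 0.732 | +0.061 | +0.045 |
| Accrual to April 2020, 3-month gap | none | 0.816 | 0.832 | 0.802 | +0.019 | −0.017 |
| | mean 3 months | 0.788 | 0.803 | 0.792 | +0.019 | +0.005 |
| | mean 6 months | 0.760 | 0.773 | 0.767 | +0.017 | +0.009 |

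The shift of #4 hardly moves down each block, while that of the symmetric cut does. Over all 128 scenarios #4 shifted the HR by +0.009 to +0.052 (log HR +0.012 to +0.063), with the same event counts as the primary in every one. With 10–20% of SoC patients starting after April 2018 the HR shift was +0.011 to +0.049. At true HRs of 0.64 and 1.00, the limits of the trial's confidence interval, the log shift was +0.017 to +0.064.

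A separate simulation with other entry dates gave shifts of 2.7% to 8.2%. The largest arose when every survivor's last contact fell on the cut-off (ln 1.082 = 0.079). With identical entry dates in both arms the shift was about zero, which confirms calendar separation as the cause.

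**The case against.** **The rule may be symmetric in practice.** The short description in Table 9 could mean a cut for everyone, and the code that settles it is not public. But the detailed rule and the limitations column both restrict it to patients without a recorded death, so the plan as written is asymmetric.

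**The asymmetry is disclosed and conservative.** The limitations column does say who is censored earlier, but not that deaths in the window still count or that the HR moves one way. A shift towards the null is conservative against a hypothesis of benefit. It is not conservative when the question is agreement with 0.80.

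**The symmetric cut has faults of its own.** This stands in part. It also moves the HR when there is no lag, because the primary rule counts deaths after the last visit and so starts at 0.81–0.83; the cut brings it back to 0.80. Its shift from the primary therefore crosses zero at some modest lag, and no change would not prove no lag. From a mean lag of about 3 months #4 lies nearer 0.80 than the symmetric cut, but only because two errors offset.

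**The consequence is small.** This stands. It is one of twelve sensitivity analyses, and the size depends on assumed accrual and visit spacing.

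**Conclusion.** The concern holds. As written, Sensitivity #4 keeps the events of the primary analysis, deletes survivors' observed time and raises the HR by nearly the same amount with or without reporting lag, so it cannot inform about lag. If lag stays within 3 months it overcorrects unless nearly all late deaths are unrecorded; with longer lag it can land near the truth by chance or undercorrect.

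The direction rests on the calendar separation that the protocol itself describes. The size rests on assumed accrual, visit gaps, lag and loss. The near-independence from lag held in every scenario tried. The shift is below one standard error and the primary analysis is not affected, so this should be corrected but does not threaten the main result.

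**What to change.** Reword the Sensitivity #4 row of Table 9 and change the code to match:

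1. Set a cut-off 3 months before the actual one for all patients. Follow-up ends at the earliest of death, last activity and the new cut-off.
2. Do not count a death after the new cut-off; censor that patient by the same rule.
3. Exclude patients whose index date falls after the new cut-off. The present row has no rule for them.
4. State that lag beyond 3 months and bias from loss to follow-up remain. With 1% monthly loss, later deaths captured and no lag, the symmetric cut still gives 0.90 for a true 0.80. State also that a small downward shift is expected when there is no lag.
5. Optionally repeat the cut at 6 months. From the 3-month to the 6-month cut the HR changes by at most 0.002 with no lag or a 1-month mean lag, and by about +0.006 to +0.026 at mean lags of 3–6 months. That comparison responds to lag and does not depend on the primary censoring rule.

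The cost is one table row, one code change and, under the assumed accrual with no lag, about 3–7% of osimertinib events and 0.7% of SoC events, in this sensitivity analysis only.
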